5.3.5 Study Subject Photographic Assessments

Site Investigators from a subset of study sites (up to 2) will take photographs of AK lesions in Subject’s treatment area on the face or scalp at baseline encounter and at Weeks 1, 2, 4 and 8, during the in-person visits. This photographic data will be used to document and depict the changes in AK lesions and LSRs that may be associated with tirbanibulin treatment in the study.

5.4 Additional Subject Assessments

5.4.1 Future Treatment Preference

Subjects and Site Investigators will be asked to state their likelihood to consider tirbanibulin to retreat AK, on a 5-point Likert scale of: 1=very unlikely, 2=somewhat unlikely, 3=neutral, 4=somewhat likely, 5=very likely). This will be assessed at Weeks 8 and 24.

5.4.2 Convenience/Ease of Use

Subjects and Site Investigators will be asked to rate the convenience/ease of use associated with tirbanibulin treatment, in comparison to other topical treatment(s), using a 5-point Likert scale of: 1: much worse; 2: somewhat worse; 3: same; 4: somewhat better; 5: much better. This assessment will be conducted among two Subject subgroups:

- Among Subjects who have experienced other topical treatments before start of tirbanibulin at baseline: At Week 8, compare rating of tirbanibulin treatment vs. previous topical treatment(s).
- Among Subjects who have been retreated with other topical treatments (other than tirbanibulin) between Week-8 and Week-24 visits: At Week 24, compare rating of original tirbanibulin treatment (at beginning of the study) vs. most recent topical treatment(s).

5.4.3 Perceptions of LSRs

The following three assessments will be conducted at Week-8 for Subjects who have experienced other topical treatments before start of tirbanibulin at baseline, and at Week-24 for Subjects who have been treated with other topical treatments (other than tirbanibulin) between Week-8 and Week-24 visits:

- Subjects and Site Investigators will be asked to rate the ‘duration of skin reactions’ associated with tirbanibulin, in comparison to other topical treatments (previous or most recent retreatment). The relative assessment will be based on a 5-point Likert scale of: 1: much longer; 2: somewhat longer; 3: the same; 4: somewhat shorter; 5: much shorter.
- Subjects and Site Investigators will be asked to rate the ‘severity of skin reactions’ associated with tirbanibulin, in comparison to other topical treatments (previous or most recent retreatment). The relative assessment will be based on a 5-point Likert scale of: 1: much worse; 2: somewhat worse; 3: the same; 4: somewhat better; 5: much better.
- Subjects will be asked to rate the ‘impact on their daily activities due to skin reactions’ associated with tirbanibulin use, in comparison to other topical treatments (previous or

most recent retreatment). The relative assessment will be based on a 5-point Likert scale of: 1: much worse; 2: somewhat worse; 3: the same; 4: somewhat better; 5: much better.

5.4.4 Unscheduled Patient Encounters

Number of unscheduled clinician encounters (via in-person clinic visits, telehealth visits and phone calls) that AK patient had in the past 8 weeks will be assessed, based on the information documented in the patient medical charts at Week 8 encounter. If the patient was retreated with tirbanibulin after week-8, we also collect this data at Week-24 timepoint.

5.5 Adherence to Treatment

Subjects will report (at Week 8) their adherence to tirbanibulin treatment by indicating the number of missed single-dose applications within the expected 5-day application period/regimen.

5.6 Safety Assessments

5.6.1 Definition of Adverse Events & Adverse Drug Reactions

An AE is any untoward medical occurrence in a patient administered a pharmaceutical product which does not necessarily have a causal relationship with this treatment. An AE can therefore be any unfavorable and unintended sign, symptom, or disease temporally associated with the use of a medicinal product, whether or not related to the medicinal product.

The Site Investigator will use the following terms to assess the severity of each AE:

- Mild: Awareness of symptoms or signs, but easily tolerated (acceptable)
- Moderate: Enough discomfort to interfere with usual activity (disturbing)
- Severe: Interferes significantly with ability to do work or usual activity (unacceptable)

A Serious Adverse Event (SAE) is any experience that suggests a significant hazard, contraindication, side effect or precaution. With respect to human clinical experience, this includes any event which:

- results in death,
- is life-threatening,

- requires inpatient hospitalization* or prolongation of hospitalization, unless hospitalization is for:
 - routine treatment or monitoring of the studied indication, not associated with any deterioration in condition.
 - elective or pre-planned treatment for a pre-existing condition that is unrelated to the indication under study and has not worsened since the start of study drug.
 - treatment on an emergency outpatient basis for an event not fulfilling any of the definitions of a SAE given above and not resulting in hospital admission.
 - social reasons and respite care in the absence of any deterioration in the subject's general condition.
- results in persistent of significant disability / incapacity, or
- is a congenital anomaly / birth defect,
- is a significant or important medical event that, based on appropriate medical judgment, may jeopardize the subject or may require intervention to prevent one of the other outcomes listed above.

* Hospitalization is defined as an overnight (in-patient) stay at the hospital or emergency room.

For all AEs (either related or not related to study medication), information about the outcome (i.e., recovered, recovering, not recovered, recovered with sequelae, fatal, unknown) and the action taken with the study treatment (i.e., drug withdrawn, dose reduced, dose increased, dose not changed, not applicable) will be documented.

Each AE, either serious or non-serious for which a causal relationship to tirbanibulin cannot be excluded, will be considered as an ADR. An ADR is an injury caused by taking medication. ADRs may occur following a single dose or prolonged administration of a medicinal product or result from the combination of two or more medicinal products. LSRs (such as: erythema, flaking/scaling, crusting, swelling, vesiculation/pustulation, and erosion/ulceration), skin scarring and pigmentation (such as: hypo- and hyper-pigmentation) as a result of application of tirbanibulin in AK treatment area will not be considered as ADRs, but will be documented separately.

The determination of whether an AE is related to study treatment (tirbanibulin) will be based on information regarding the degree to which the study treatment had caused or contributed to the event and will be categorized per the following criteria:

- Related: There were good reasons and sufficient information (e.g. plausible time sequence, dose-response relationship, pharmacology, positive de-challenge and/or re-challenge) to assume a causal relationship with the study medication in the sense that it is plausible, conceivable or likely.
- Not Related: There were good reasons and sufficient information (e.g. implausible time sequence and/or attributable to concurrent disease or other drugs) to rule out a causal relationship with the study medication.

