6.6.9 Safety Assessments

The safety data will be analyzed descriptively using Safety Population dataset (if it is different from FAS), to report the frequency of occurrences of AEs, SAEs, ADRs, and LSRs. These will be reported at individual item level as well in aggregate at relevant category level for Week 8

post-index date. The number of patients discontinuing treatment within the 8-week post-index date because of AEs, ADRs and for any other reasons will be reported, as documented in patient medical charts.

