Note: Data from Clinician DCF; X patients had missing data; The denominator for the percentages is the number of patients with available data (N=X). This concomitant non-AK medication use correspond to use of medications at any time during the study observation period, overlapping with Klisyri® medication use.

Table 4.11 Patient Disposition Throughout the Study

	Baseline n (%)		Week 8 n (%)		Week 24 n (%)	
	Patient Survey	Clinician Survey	Patient Survey	Clinician Survey	Patient Survey	Clinician Survey
(Cumulative numbers)						
Patients completing study visit						
Patients with missing surveys						
Patient Terminations/ Discontinuations						
P1Br3 Due to Adverse event associated with any medication (other than tirbanibulin (Klisyri®)						
P1Br4 Due to Adverse drug reaction associated with tirbanibulin (Klisyri®)						
P1Br5 Due to Clinician decision: tirbanibulin (Klisyri®) treatment non-compliance						
P1Br6 Due to Clinician decision, Other [P1Br6oe]						
P1Br2 Patient voluntarily withdrawal of consent (for reasons other than adverse event or adverse drug reaction)						
P1Br1 Patient Lost to follow-up						
TOTAL Study Population (N)	300	300	300	300	300	300

Table 4.12 Reason for Discontinuation

Statistics	Adverse drug reaction associated with tirbanibulin (Klisyri®)	Adverse event associated with any medication (other than tirbanibulin (Klisyri®))	Clinician decision: tirbanibulin (Klisyri®) treatment non-compliance	Clinician decision, Other	Patient voluntarily withdrawal of consent (for reasons other than adverse event or adverse drug reaction)	Patient Lost to follow-up	TOTAL
Week 8	n (%)						
Week 24	n (%)						
TOTAL	n (%)						

Table 4.13 Subject Level Summary of Local Site Reactions

LSRs (Refer to annotated CRF for all other variables)	Baseline N=X	Week 8 N=X	Week 24* N=X
LSR1 Erythema (N=X)			
LSR1r1 Grade			
2. Mild	n (%)	n (%)	n (%)
3. Moderate	n (%)	n (%)	n (%)
4. Severe	n (%)	n (%)	n (%)
LSR1r4 Action taken with Tirbanibulin			
1. Drug withdrawal	n (%)	n (%)	n (%)
2. Dose Reduced	n (%)	n (%)	n (%)
3. Dose Increased	n (%)	n (%)	n (%)
4. Dose not changed	n (%)	n (%)	n (%)
5. Not Applicable	n (%)	n (%)	n (%)
LSR2 Flaking/Scaling (N=X)			
Grade			
Mild	n (%)	n (%)	n (%)
Moderate	n (%)	n (%)	n (%)
Severe	n (%)	n (%)	n (%)
Action taken with Tirbanibulin			
Drug withdrawal	n (%)	n (%)	n (%)
Dose Reduced	n (%)	n (%)	n (%)
Dose Increased	n (%)	n (%)	n (%)
Dose not changed	n (%)	n (%)	n (%)
Not Applicable	n (%)	n (%)	n (%)

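### The disposition tables have no local-skin-reaction reason for leaving the study, and Table 4.13 gives no once-per-patient count of reactions that led to withdrawal

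*SAP*

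**What the plan says.** SAP 5.6.1, like protocol 8.5.1, takes erythema, scaling, crusting, swelling, vesiculation, erosion, scarring and pigment change caused by tirbanibulin out of the ADR category. These "will not be considered as ADRs, but will be documented separately".

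SAP Table 4.11 lists six reasons for termination, and Table 4.12 uses the same six. Some labels below are cut just before a closing mark.

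- The adverse-event reason is worded "P1Br3 Due to Adverse event associated with any medication (other than tirbanibulin (Klisyri", so it does not reach the study drug.
- P1Br4 is for an ADR to the study drug.
- P1Br5 is for a decision by the clinician because the patient did not comply.
- The residual clinician code is "P1Br6 Due to Clinician decision, Other [P1Br6oe", which carries a free-text field.
- The voluntary code is "P1Br2 Patient voluntarily withdrawal of consent (for reasons other than adverse event or adverse drug reaction", with no free-text field shown.
- P1Br1 is for loss to follow-up.

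SAP 6.6.9 promises the number of patients stopping treatment within 8 weeks of the index date: those stopping "because of AEs, ADRs and for any other reasons will be reported". It does not name LSRs as a reason for stopping, although it does list them among the events whose frequency is reported.

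Table 4.13 gives grade and action taken with tirbanibulin, including drug withdrawal, for LSR1 to LSR6. For LSR7 to LSR9 (scarring and the two pigment changes) it records only whether the reaction is present. Table 4.14 lists each LSR by patient ID, with the action taken.

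**The concern.** Tolerability and the effect of LSRs are both stated objectives (SAP 2.1), and LSR frequency is a named endpoint (SAP 2.2). The protocol's background section argues for the product partly on milder skin reactions. Readers will therefore ask how many patients gave up because of skin reactions.

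The disposition tables are where they will look. Separating LSRs from ADRs is a legitimate choice, but the reason list still works as if a tirbanibulin ADR were the only drug-related cause of leaving. Patients who leave because of an LSR would then be tallied with administrative or personal reasons. The tirbanibulin ADR line could read zero even though some patients had left because of the drug's effect on the skin.

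**Working it through.** The documents give no withdrawal rate, and there is no plan figure to reproduce. The check sets the definition against the table shells.

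**1. Where can a study termination caused by an LSR be coded?**

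| Reason | Does a tirbanibulin LSR fit? |
|---|---|
| P1Br3, adverse event | No: limited to medications other than tirbanibulin |
| P1Br4, tirbanibulin ADR | No: SAP 5.6.1 says LSRs are not ADRs |
| P1Br5, clinician decision on non-compliance | Only if recorded as non-compliance |
| P1Br6, other clinician decision | Possible, identifiable only from free text |
| P1Br2, voluntary withdrawal | Doubtful (see below) |
| P1Br1, lost to follow-up | Only if the patient cannot be reached |

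Reasons naming an LSR: 0 of 6. The two reasons that name an adverse event or ADR as the cause both exclude a tirbanibulin LSR, one by its wording and one by definition. Each of the other four is a non-drug label.

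P1Br2 is doubtful because its wording also excludes adverse events, and SAP 5.6.1 removes LSRs from ADRs without removing them from its broad definition of an AE. Read strictly, a patient who withdraws consent because of an LSR has no correct code. In practice the site must choose one.

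**2. What does Table 4.13 count?**

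- Items with a drug-withdrawal row: LSR1 to LSR6, so 6 of 9.
- Items without one: LSR7 to LSR9, so 9 − 6 = 3.
- Rows counting patients with any LSR that led to withdrawal: 0.

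Let w₁ to w₆ be the six drug-withdrawal counts in one time column, and U the number of distinct patients behind them. A patient may contribute to one row or to all six, so

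max(w₁, …, w₆) ≤ U ≤ w₁ + … + w₆.

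Because one patient can fill up to six rows, the sum can overstate U by a factor of up to six. The printed table cannot narrow this range.

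**3. How do the LSR rows compare with the AE and ADR rows?**

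Tables 4.15, 4.16 and 4.18 are at subject level and use one action row that covers both withdrawal of the drug and discontinuation from the study. The LSR rows in Table 4.13 cover withdrawal of the drug only. An LSR that leads a patient to leave the study therefore has no row in Table 4.13 and no reason in Table 4.12.

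**4. Is a reason for stopping recorded elsewhere?**

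For a retreatment course, Table 2.38 has separate codes for stopping because of side effects and because of intolerance. For the original 5-day course, Tables 2.6 and 4.7 record only whether it was completed, with no reason.

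**The case against.** The strongest reply is that the SAP does document LSRs separately, as it says it will. Table 4.13 reports drug withdrawal for each of the six graded reactions, and Table 4.14 ties the action to a patient ID. P1Br6 has free text, SAP 6.6.9 reaches any other reason, and protocol 6.4.2 and 7.6 require the reason for withdrawal to be recorded. A once-per-patient count of drug withdrawal for LSR1 to LSR6 can be built from Table 4.14.

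All of that stands, and it limits the point. A reader might infer that stopping because of an LSR has no category anywhere and is hidden. The documents do not support that for stopping the drug. A reader might also infer that every patient who stops because of an LSR will appear in Table 4.12 under a non-drug reason. That does not follow either. Treatment lasts 5 days and follow-up 24 weeks, so a patient can stop the ointment, remain in the study and never enter Table 4.12. Nor do the documents define a headline tolerability count from which LSRs are left out.

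The reply does not cover leaving the study. Neither Table 4.13 nor Table 4.14 records study termination, and free text under one of six codes is not a summary. Table 4.14 is a listing, so the reader would have to construct the patient total.

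**Conclusion.** The point holds as a reporting gap in two places. First, Tables 4.11 and 4.12 have no LSR reason, so a study termination caused by an LSR is counted under a non-drug reason. Second, Table 4.13 counts LSR-driven drug withdrawal by reaction type only and gives no patient total.

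The size in patients is unknown, because the documents give no expected rate. If nobody leaves the study because of an LSR, the first gap changes no number. If nobody stops the drug because of one, the second changes none.

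The conclusion rests on two assumptions: that Tables 4.11 and 4.12 describe leaving the study, as their consent-withdrawal and lost-to-follow-up reasons suggest, and that sites apply the SAP 5.6.1 definition when choosing a code. If some sites enter LSRs under P1Br4 anyway, that line mixes two definitions.

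The primary and secondary endpoints are not affected. The change should be made before the safety tables are produced, because tolerability is a stated objective.

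**What to change.** 1. In Table 4.13, add a row for subjects with at least one LSR leading to withdrawal of the drug or discontinuation from the study, each counted once. The existing action-taken fields for LSR1 to LSR6 supply the drug-withdrawal part. The study-discontinuation part comes from step 3. Footnote that LSR7 to LSR9 have no action field.
2. In SAP 6.6.9, name LSRs alongside AEs and ADRs, and report a combined count of patients who discontinued because of an ADR or an LSR. State stopping treatment and leaving the study as separate figures.
3. In Tables 4.11 and 4.12, add a local skin reaction in the treated area as a reason. If the eDCF is still open, add it as a P1B option. If not, reclassify from the P1Br6 free text, the documented withdrawal reasons and the Table 4.14 data, under a rule written before the tables are run.

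The drug-withdrawal part of step 1 needs programming only. Step 3 needs either one form option or a review of withdrawal records, with site queries where the record is unclear. Patients lost to follow-up may remain unclassifiable. The one downside for the sponsor is that the tolerability figure may look slightly less favourable.

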6 STATISTICAL CONSIDERATIONS

Detailed plans for the statistical methods will be provided in a Statistical Analysis Plan (SAP) which will be finalized prior to database lock.

6.1 Sample Size Considerations

No formal sample size and power calculations were undertaken. Considering the descriptive nature of the study and the feasibility of recruiting the study population, approximately 300 study Subjects from across a maximum of 50 clinical sites for the entire study has been identified as a sample to guide the planned analysis addressing the study objectives.

6.2 Analysis Populations and Datasets

Statistical analysis and data tabulation will be performed using the following analysis populations unless specified otherwise:

- Safety Population: All patients who received at least one dose of tirbanibulin during the study observation period of 8-weeks related to primary endpoint, as part of usual care.
- Full Analysis Set (FAS): All patients within the Safety Population that had at least some data pertaining to the key variables studied at relevant timepoints, post-baseline.

All safety evaluations (part of additional objectives) will be conducted among the safety population, while FAS will be used to conduct analyses addressing rest of the study objectives, including the primary objective.

6.3 General Statistical Procedures

6.3.1 Overview

Data from Site Investigators and study Subjects will be combined into one dataset. No site-specific analyses will be conducted. Validated instruments will be scored according to developer guidelines, reporting domain scores and overall summary scores, as appropriate. EPQ and other ad hoc questions will be analyzed and reported individually, based on the respective response scales. For all outcome measures, the analyses will focus on baseline, Week-8 and Week-24, as applicable.

All statistical analyses will be based on all available data assuming that all missing data are uninformative and will be conducted using appropriate statistical software, such as SAS. An interim analysis will be conducted after the completion of 8 weeks of data collection for all study Subjects. The final study analyses will be conducted after the completion of 24 weeks of data collection for all study Subjects.

